## Resources

If this study is a collaborative UM/VA study, please clarify which resources are being used at each institution.

1 \* **Describe the time that the Principal Investigator will devote to conducting and completing the research:**

[name] will be devoting 35% effort to this research project, the work is slotted for support by a VHA eSPIRE research grant.

2 \* **Describe the facilities where research procedures are conducted:**

VA Maryland Health Care System.

This study consists of three phases: focus group, pre-pilot, and pilot phases.

The focus group study will occur at the Loch Raven VA where there is a GEROFIT exercise program. We have previously met informally with some Veterans in this program as part of preparatory to research queries. This facility include a gym and meeting space. We will meet with the focus group Veterans in the meeting space adjacent to the gym.

The pre-pilot phase will involve one-on-one interviews with Veterans. The Veterans will be recruited from the Empower Veterans Program, meeting at the Loch Raven VA, and from the Women's clinic at Fort Meade. The Veteran will be invited to attend a one-on-one interview session at the VAMHCS main hospital. The GRECC is based there and there are private counseling rooms available for these sessions. In the event that the study participant is not comfortable with coming to the VAMHCS main building, we will identify alternative sites that meet the criteria for the participant's comfort and privacy.

The pilot phase will involve one-on-one interviews with Veterans as well as phone interviews. The Veteran will be invited to attend a one-on-one interview sessions at the VAMHCS main hospital. The GRECC is based there and there are private counseling rooms available for these sessions. In the event that the study participant is not comfortable with coming to the VAMHCS main building, we will identify alternative sites that meet the criteria for the participant's comfort and privacy.

This research project is based in the Maryland VA GRECC located in 4B area of the VAMHCS main building. The PI and co-investigators have dedicated office and meeting space as well as computational resources and access to statistical consulting.

3 \* **Describe the availability of medical and/or psychological resources that subjects might need as a result of anticipated consequences of the human research:**

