## Study Procedures

**If you uploaded a separate research protocol document in the 'Research Protocol' page, cite the applicable section and page numbers from that document in the answer boxes below. (If this study is a collaborative UM/VA study please list each procedure that is being conducted and the locations where it is being conducted.)**

1 \* Describe all procedures being performed for research purposes only (these procedures would not be done if individuals were not in the study) and when they are performed, including procedures being performed to monitor subjects for safety or to minimize risks:

Patients will be recruited from multiple clinics and intentionally include older and female Veterans. The study coordinator will recruit and consent Veterans. There are three study groups including focus group, one-on-one interview group, and pilot study group. Veterans will be recruited separately for each of these study groups, necessitating separate consent forms.

Procedures:

Phase 1: Veteran focus group

- Single occasion, focus group discussion: Up to five Veterans, recently graduated from the Empowering Veterans Program at the Baltimore-Loch Raven VA will meet during the first quarter of funding for this program. The group will be introduced to the prototype App on tablet computers. Using open semi-structured interviews, we will explore their use of non-pharmacological pain self-management strategies, with special attention to understanding use of language and how existing strategies link to labels and the values they associate with each. A total of five interface options will be included, to assess appeal, perceived navigability of these options, and input on design features and usability. Brief questionnaires will be completed at the end of the focus group session and compensation for participation will be distributed. (Site: Loch Raven VA)

Phase 2: Veteran Pre-pilot group

- Single one-on-one interview: Using open semi-structured interviews, we will explore their use of non-pharmacological pain self-management strategies, with special attention to understanding use of language and how existing strategies link to labels and the values they associate with each. A total of five interface options will be presented to the interview subjects and rated for appeal, perceived navigability, design features, and usability. Validated questionnaires will be completed, see details below. Compensation for participation will be distributed.

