- o Five Veterans from Empowering Veterans Program at the Baltimore-Loch Raven VA; (Site: Loch Raven VA)
- o Five female Veterans from the Women's health clinic; (Sites: Baltimore VAMHCS and Fort Meade VA)

Our pre-pilot objective is to reach two groups of Veterans: 1) 5 Veterans completing the EVP (Empower Veterans Program) and 2) 5 Veterans attending the Women's Health Clinic, in collaboration with [name], Director of Women's Health for VAMHCS. This will provide important feedback for the experience of two different groups: the first group is experienced with non-pharmacological, values-based, approaches to pain management including CBT, ACT, MBSR, and others. The Women's Health Clinic group may not have had formal exposure to non-pharmacological pain management and may require additional information or resources to attain maximal benefit from C-MEPPS. The goal is an App that is useful to the broadest number of Veterans. We will include at least 4 older Veterans among the 10 recruited so the App can be developed with input from older Veterans accessing whole-health integrative approaches to pain self-management.

Phase 3: Veteran Formal pilot testing group

- Multiple visits, phone interviews, and activity monitoring. Once feedback from the pre-pilot group is obtained and further modifications incorporated into READY-GO Pain, the App will be tested with a pilot group.
- 20 Veterans with cLBP a balance of middle-aged and older male and female veterans.
- The study procedures will include:
  - o Recruitment: the study will be introduced to potential study subjects by the PI, study investigators, colleagues, or the study coordinator
  - o Consent: the study will be described in detail to the potential study subjects by PI, study investigators, or the study coordinator. If the study subject agrees to participation, they will be given a pain diary to bring back at the time of the initial visit in 2 weeks time.
  - o Initial visit: the study subject will be introduced to the tablet App and instructed in use, all questions will be answered. The study subject will complete brief questionnaires pertaining to pain, sleep, quality of life, prior App experience, and pain interference. The study subject will be fitted with an actigraph and instructed in the use of the device. A 6-minute walk test will be completed. The Veteran will be given the tablet, loaded with the App, to take home and bring back at the follow-up and final visits.

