  - o 1st followup phone call: The study subject will be contact by phone one week after the initial visit. Coaching on App use and troubleshoot of App and actigraph use will be provided. Brief pain and pain interference questionnaires will be administered.
  - o 1st follow up visit: the study subject will be coached regarding the tablet App and actigraph use, all questions will be answered. The study subject will complete brief questionnaires pertaining to pain, sleep, quality of life, prior App experience, and pain interference. The study subject will be fitted with an actigraph and instructed in the use of the device.
  - o 2nd followup phone call: The study subject will be contact by phone 3 weeks after the initial visit. Coaching on App use and troubleshoot of App and actigraph use will be provided. Brief pain and pain interference questionnaires will be administered.
  - o 3rd followup phone call: The study subject will be contact by phone 4 weeks after the initial visit. Coaching on App use and troubleshoot of App and actigraph use will be provided. Brief pain and pain interference questionnaires will be administered.
  - o 4th followup phone call: The study subject will be contact by phone 5 weeks after the initial visit. Coaching on App use and troubleshoot of App and actigraph use will be provided. Brief pain and pain interference questionnaires will be administered.
  - o Final visit, in person 6 weeks after the initial visit: the study subject will be debriefed regarding tablet App, all questions will be answered. The study subject will complete brief questionnaires pertaining to pain, sleep, quality of life, prior App experience, and pain interference. The study subject will be debriefed on use of the Actigraph device. The devices will be collected. A 6-minute walk test will be completed.
  - o Final follow up phone call: The subject will be briefly interviewed two weeks after final visit for final thoughts about the App use experience and any plans to change behaviors as a result of using the App for activity planning.
  - o Veterans from Empowering Veterans Program at the Baltimore-Loch Raven VA; (Site: Loch Raven VA)
  - o Female Veterans from the Women's health clinic; (Sites: Baltimore VAMHCS and Fort Meade VA)

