## Sample Size and Data Analysis

**If you uploaded a separate research protocol document in the 'Research Protocol' page, cite the applicable section and page numbers from that document in the answer boxes below.**

1 \* Provide the rationale and sample size calculations for the proposed target population:

This study is not powered to find statistically significant differences. Qualitative data interpretation will follow from a priori hypothesis development, in brief: specific design features, e.g. simple design, clear navigation, will improve Veteran experience. Quantitative aspects are not anticipated to attain statistical significance and will be descriptive.

2 \* Provide the plan for data analysis. Include in the description the types of comparisons that are planned (e.g., comparison of means, comparison of proportions, regressions, analysis of variance, etc.), which is the primary comparison/analysis, and how the analyses proposed will relate to the primary purposes of the study:

Both qualitative and quantitative methods of research analysis will be used. Data analysis will be performed utilizing a standard statistical analysis package, SAS and excel will be used to evaluate program development, implementation, qualitative instrument development, complex analytical methods, mixed methods research, and survey methodology.

Qualitatively, the current pilot study is designed to identify common barriers to App use.

Quantitatively, this study will obtain statistical information to guide the development of outcome measures for a Merit-level research proposal to determine the potential effectiveness of this multi-dimensional approach to pain self-management in an App.

ID: VIEW4E02806052800  
Name: v2\_Sample Size and Data Analysis

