## Prospective Data

You indicated that the study involves the collection of prospective data.

1 \* Where is the data being collected from? (Check all that apply)

- Medical records
- Medical images
- Commercial (for profit) entity
- Publicly available records
- Schools
- Other

1.1 If Other, please specify:

Study surveys, observations, actigraphy, and tablet utilization data

2 \* What data fields will you have access to/collect for the study? For example, name, initials, date of birth, Social Security number, income, demographic information, family units, housing, etc.

Name, date of birth, gender, race, ethnicity.

6 minute walk test observation, actigraph recording, use of tablet data

You can also upload a copy of the data fields/variables to be collected for the study:

Name	Created	Modified Date
------	---------	---------------

There are no items to display

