## Recruitment

1 \* **Describe plans for recruitment, including the identification of potential participants (or acquisition of charts/records/samples) and initial interactions with them: (If this study involves the VA please list all sites at which recruitment will take place.):**  
 Veterans will be recruited from the following clinical populations: Empower Veterans Program, GEROFit participants, Women's health clinic, VAMHCS patients with LBP meeting eligibility criteria.

Recruitment will take place at Baltimore, Loch Raven, Annex, and Fort Meade locations of VAMHCS. Potential VA participants will be identified by several methods: (1) CPRS chart review and screening via use of a partial HIPAA waiver, (2) VA clinician referrals of participants who meet inclusion criteria and who might be interested in participating, (3) Self referrals by participants who hear about the study and are interested in participating or who have participated in other studies and have indicated a willingness to be contacted for studies in the future.

We would also like to perform a computer-based screening using the VISN 5 Corporate Database Warehouse to screen for individuals who have had low back pain for at least three months. As part of this, we will use a data pull with real Social Security Numbers (SSNs) from VA's Information and Computing Infrastructure (VINCI) to enhance recruitment goals within the VISN. Potential subjects from the VISN will be mailed an IRB approved recruitment letter (uploaded in recruitment section), as well as an opt in/opt out post-card (uploaded in recruitment section). Postage will be provided on the opt in/out post-card, which will allow for potential subjects to indicate whether they

would like to be contacted in the future related to the study. The opt in/out post-card will not list the subject's name, but rather will only provide a letter number that we will generate and store in a password protected file on the VA server prior to mailing the letter. If no response is received within two weeks, we will follow up with a phone call to gauge subject interest.

Per VA requirements, initial contact with potential veteran participants will be made in person or by letter prior to any telephone contact. Specifically, we will approach individuals before or after their VA appointments.

2 \* **Describe measures that will be implemented to avoid participant coercion or undue influence (if not applicable to the study, enter "N/A"):**

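### Does the protocol give two conflicting recruitment populations for the Phase 3 pilot, and lose track of prior Empower programme attendance?

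*Protocol*

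**What the plan says.** Study Procedures, item 1, opens with a general statement on recruitment: "Patients will be recruited from multiple clinics and intentionally include older and female Veterans". It then describes three separately recruited groups. Phase 1 is a focus group of up to five Empower programme graduates. Phase 2 is ten one-on-one interviews, five with programme Veterans and five with female Veterans from the Women's clinic. Phase 3 is the pilot of 20 Veterans, meant to balance men and women and middle-aged and older Veterans.

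The Phase 3 procedure list runs from recruitment to the final phone call and then ends with two bullets that are not procedures: "Veterans from Empowering Veterans Program at the Baltimore-Loch Raven VA", and female Veterans from the Women's clinic.

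Recruitment, item 1, covers the whole study and assigns no source to a phase. It names the Empower programme, GEROFit, the Women's clinic and "VAMHCS patients with LBP meeting eligibility criteria". It adds a search of a regional database to "screen for individuals who have had low back pain for at least three months", followed by a letter and a reply card.

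On prior exposure, the Phase 2 text says programme Veterans already know non-drug approaches, while Women's clinic Veterans "may require additional information or resources to attain maximal benefit from C-MEPPS". Prospective Data, item 2, lists "Name, date of birth, gender, race, ethnicity", the walk test, actigraphy and tablet use. Sample Size and Data Analysis, item 2, states the qualitative aim: "Qualitatively, the current pilot study is designed to identify common barriers to App use".

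**The concern.** A reader who takes the Phase 3 bullets as the full source list gets a different pilot population from a reader of the Recruitment section. One of the two bulleted sources is female only, so every man in the pilot would come from the Empower programme. Usability and barrier findings for men would then say little about men without that training.

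The wider list raises a second worry. Trained and untrained Veterans are mixed, and if attendance is not recorded, barriers met by one group cannot be separated from barriers met by the other. The protocol itself treats earlier exposure as relevant to what a Veteran needs from the App. A later analysis plan could not recover a characteristic that nobody had collected.

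**Working it through.** **1. Enrolment, reproduced.** Phase 1 (up to 5) + Phase 2 (5 + 5) + Phase 3 (20) = 35, the figure in Participant Selection. Phases 1 and 2 account for 15 places with named sources, so the question concerns 35 − 15 = 20 places, and 20/35 = 57%. This is Phase 3's share of enrolment, not a measure of harm.

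**2. What the strict reading would imply.** If the two bullets were the only Phase 3 sources, the smallest possible programme share would be the number of men divided by 20. The protocol gives no number of men, so a range is assumed:

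| Men among 20 (assumed) | Minimum programme share, bullets read as complete | Programme share under Recruitment |
|---|---|---|
| 8 | 8/20 = 40% | 0% to 100% |
| 10 | 10/20 = 50% | 0% to 100% |
| 12 | 12/20 = 60% | 0% to 100% |

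Men from outside the programme would number 0 on the strict reading and, with 10 men assumed, anywhere from 0 to 10 on the wider one. The ranges overlap, so the texts need not lead to different samples.

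**3. Can the extra sources belong to another phase?** Largely not. Phase 1 is confined to programme graduates. Phase 2 is confined to the programme and the Women's clinic, and the Resources section agrees for the pre-pilot phase: "The Veterans will be recruited from the Empower Veterans Program, meeting at the Loch Raven VA", with the Women's clinic as the second source. General low back pain patients and mailing respondents therefore fit only Phase 3. GEROFit is less clear, because Resources places the focus group at the GEROFit site.

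**4. Are the two bullets a deliberate restriction?** The evidence points the other way.
- They match the Phase 2 bullets with the number five removed, and they follow the last phone call in a list of procedures.
- Two parallel accounts of Phase 3, in Justification, Objective, & Research Design (item 2) and in Behavioral Intervention (item 1), have no such lines.
- They contain no word such as *only*, and both sources are among the four in Recruitment.
- The Phase 3 recruitment bullet says who introduces the study and restricts nobody. The opening of the same section speaks of several clinics.

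**5. Is attendance shown to be unrecorded?** It is absent from the questionnaire list and from the Prospective Data field list. But that field list is plainly incomplete: item 1 of the same page names study surveys as a source, yet item 2 lists no survey variable. Forms that could hold attendance or recruitment route are uploaded but not shown: the phone screen, the follow-up interview script, the eligibility checklist and the pain self-management change assessment. The Protected Health Information section links each study number to a name and gives medical records as a source, so attendance may also be recoverable from the chart.

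**6. Does any planned analysis need it?** No. Sample Size and Data Analysis calls the study unpowered and its quantitative part descriptive, and it plans no comparison by prior training.

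**The case for a change.** The best case for a change is that the stray lines sit under Phase 3 in the operative procedures section, and that neither parallel account of Phase 3 names a source to correct them. The recruitment letter and reply card were uploaded on 31 May 2022, so the mailing looks like a live plan whose recipients have no stated place in the procedures text. The protocol contrasts experienced and inexperienced Veterans and wants an App of wide use. A yes/no question at the initial visit would cost almost nothing, and data not collected cannot be supplied later.

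The mismatch stands, and so does the inference that general patients and mailing respondents belong to Phase 3. The harm does not. It needs a probable copying remnant to be followed as exhaustive, against both the Recruitment section and the opening of Study Procedures. The description of programme Veterans as experienced is also borrowed from Phase 2; the Phase 3 line says only that they come from the programme.

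The attendance item would be a reasonable extra, but it is a preference. Prior exposure is deliberately sampled in Phase 2, whose feedback shapes the App before the pilot. A mixed Phase 3 group suits an App meant for many kinds of Veteran. Splitting 20 people by an uncontrolled characteristic would give small groups that support little beyond individual description.

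**Conclusion.** No change to the plan follows. The two sections differ on paper over the sources for 20 of 35 places, and the likeliest explanation is Phase 2 text carried into Phase 3. A coordinator working from the Recruitment section would recruit from all its sources, and nothing in the Phase 3 lines forbids that. Stating the Phase 3 sources once would be tidier, but it is editorial and alters no sample size, estimate or error rate in a descriptive pilot.

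The claim that barriers could not be told apart by prior training is not established, because the forms most likely to record attendance are not shown and records are linkable to the chart. A breakdown by attendance is optional. This conclusion rests on reading the two lines as a remnant. If the investigator in fact means to limit Phase 3 to those two sources, the Recruitment section would be the text out of line, and the 40% to 60% minimum programme share (for an assumed 8 to 12 men) would describe the pilot. Nothing in the protocol points to that intention.

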## Sample Size and Data Analysis

**If you uploaded a separate research protocol document in the 'Research Protocol' page, cite the applicable section and page numbers from that document in the answer boxes below.**

1 \* Provide the rationale and sample size calculations for the proposed target population:

This study is not powered to find statistically significant differences. Qualitative data interpretation will follow from a priori hypothesis development, in brief: specific design features, e.g. simple design, clear navigation, will improve Veteran experience. Quantitative aspects are not anticipated to attain statistical significance and will be descriptive.

2 \* Provide the plan for data analysis. Include in the description the types of comparisons that are planned (e.g., comparison of means, comparison of proportions, regressions, analysis of variance, etc.), which is the primary comparison/analysis, and how the analyses proposed will relate to the primary purposes of the study:

Both qualitative and quantitative methods of research analysis will be used. Data analysis will be performed utilizing a standard statistical analysis package, SAS and excel will be used to evaluate program development, implementation, qualitative instrument development, complex analytical methods, mixed methods research, and survey methodology.

Qualitatively, the current pilot study is designed to identify common barriers to App use.

Quantitatively, this study will obtain statistical information to guide the development of outcome measures for a Merit-level research proposal to determine the potential effectiveness of this multi-dimensional approach to pain self-management in an App.

ID: VIEW4E02806052800  
Name: v2\_Sample Size and Data Analysis

